### 1. INTRODUCTION

# 1.1. Background Information and Study Rationale

# 1.1.1. Background Information

Psoriasis is a common, chronic relapsing inflammatory skin disease (Parisi, 2012) with recurrent episodes of prominently erythematous and scaly patches (plaques). Approximately 2% to 3% of the global population is affected by psoriasis; those affected are predominantly adults, who are most often diagnosed between the ages of 18 to 35 years. Psoriasis disrupts daily activities such as work and/or school attendance, interpersonal relationships, recreational activities, and intimacy, thereby significantly impacting sufferers' quality of life. Furthermore, psoriasis sufferers can also have co-morbidities such as arthritis, depression, inflammatory bowel disease, and cardiovascular (CV) diseases.

Up to 80% of patients have mild to moderate plaque-type psoriasis, which is generally managed with topical treatments. The most commonly used treatments for psoriasis include topical corticosteroids and vitamin D analogs, alone or in combination. Vitamin D analogs are moderately efficacious as monotherapy, whereas application of topical corticosteroids, particularly the very potent ones, is restricted in terms of body areas that can be treated and the duration of use due to the well-known application site and systemic adverse drug reactions (Mason, 2013). Although numerous topical treatment options are available, there remains a need for a topical treatment that combines a high level of efficacy with an acceptable safety profile and permits application to a large body surface area (BSA) without restrictions on duration of treatment.

Tapinarof (DMVT-505), formerly known as GSK2894512, is a fully synthetic hydroxylated stilbene that is being developed by Dermavant Sciences GmbH (Dermavant) as a novel anti-inflammatory agent for the topical treatment of atopic dermatitis (AD) and plaque psoriasis. The compound (number WBI 1001) was initially developed by Welichem Biotech Inc. (Welichem; Burnaby, British Columbia, Canada) and then was acquired by GlaxoSmithKline (GSK) on 31 July 2012 for further development in the rest of the world except China. Beijing Wenfeng Tianji Pharmaceuticals (BWTP) is developing a compound in China identified as Benvitimod (active ingredient corresponds to tapinarof) with a unique topical formulation. Dermavant acquired the drug from GSK on 20 August 2018 for continued development.

Tapinarof cream, 1% is a white to off-white, oil-in-water emulsion intended for topical application to AD and psoriatic skin lesions, which has a novel mechanism of action. The drug likely mediates its effects via the aryl hydrocarbon receptor (AhR) agonist and nuclear factor erythroid 2-related factor 2 (Nrf2) because the pattern of pro-inflammatory mediators inhibited by tapinarof is different from that of corticosteroids, calcineurin inhibitors, vitamin D analogs, and other immunosuppressive agents commonly used to treat AD and psoriasis. Rather, the profile of biological responses elicited by tapinarof most closely matches that of the dual activation properties of coal tar, a common nonprescription treatment for psoriasis. Together, existing data identify tapinarof as a non-steroid, therapeutic AhR-modulating agent (TAMA), which is a unique mechanism of action compared with existing therapies.

Tapinarof cream has been evaluated in nonclinical studies at concentrations up to 8% and in clinical studies at concentrations up to 2%. Three Phase 1 clinical pharmacology studies in healthy volunteers and 7 Phase 1/2 studies in subjects with AD and psoriasis have been

Clinical Study Protocol - Version 2.0

completed. Refer to the current version of the tapinarof Investigator's Brochure for detailed information. Tapinarof has demonstrated an acceptable safety profile and a clear therapeutic effect, as compared with vehicle, in both psoriasis and AD.

Four randomized, double-blind, vehicle-controlled, clinical studies to evaluate the safety and efficacy of topically applied tapinarof cream in subjects with AD or psoriasis were conducted by Welichem; one 28-day and one 12-week study was completed for each indication.

These studies enrolled a total of 282 adult subjects, with 235 subjects exposed to tapinarof cream, 0.5%, 1%, or 2% (Formulation C) once or twice daily for a period of 28 to 84 days. Efficacy was rapid, and statistically significant differences versus vehicle were observed as early as Day 14 for the majority of efficacy parameters in both indications. The most frequently reported (1% to 6% of 235 subjects) dermatological adverse events (AEs), regardless of causality, were application site discoloration/hyperpigmentation, application site dermatitis, papular rash, pruritus, dermatitis contact, folliculitis, erythema, and skin burning sensation. Nasopharyngitis and headache were the most frequently reported (> 10% of subjects) nondermatological AEs overall. Overall, results of the clinical studies indicated tapinarof was highly efficacious for both AD and psoriasis, with a favorable safety profile.

The first clinical study with Formulation F (Study 201851) was a Phase 1 study to evaluate the systemic exposure and pharmacokinetic (PK) parameters of tapinarof cream, 1% and 2%. This study was conducted in 11 subjects with AD; 5 subjects were treated with the 2% dose and 6 subjects were treated with the 1% dose. Headache was the most frequently reported (100% and 60% of subjects at the 1% and 2% doses, respectively) nondermatological AE.

Two Phase 2b, 12 week, randomized, double-blind, vehicle-controlled, 6-arm, parallel group, dose-finding studies with topically applied tapinar of cream were conducted by GSK; 1 study each in subjects with AD or psoriasis. These 2 studies evaluated the safety and efficacy of tapinarof cream (Formulation F) at 2 concentrations (0.5% or 1%) and 2 application frequencies (once daily or twice daily) in 247 adult and adolescent subjects with AD and in 227 adult subjects with plaque psoriasis. In both studies, tapinarof showed a clear therapeutic effect compared with vehicle, with the 1% concentration treatment groups demonstrating a higher proportion of subjects with treatment success compared with the 0.5% concentration groups (applied once daily and twice daily in the AD study). In both indications, the tapinar of 1% dosing groups showed a faster onset of action than the 0.5% dosing groups, and once daily application had similar efficacy to twice daily application. In both Phase 2b studies, tapinarof showed an acceptable safety profile. Treatment-emergent adverse events (TEAEs) were reported with a higher frequency in the tapinar of groups than in the vehicle groups. The most frequent TEAEs (≥ 5% in any arm or in total) were nasopharyngitis, folliculitis, dermatitis contact, atopic dermatitis, upper respiratory tract infection, headache, vomiting, acne, application site dermatitis, miliaria, dermatitis allergic, and impetigo. The majority of TEAEs were mild or moderate in severity. In each study, the tapinar of 1% once daily treatment group had a lower frequency of TEAEs than the tapinar of 1% twice daily treatment group.

### 1.1.2. Study Rationale

This pivotal Phase 3 study is being conducted as part of a clinical development program to evaluate the efficacy and safety of tapinarof cream, 1% for the topical treatment of plaque psoriasis in adults with psoriasis. The results of this study are intended to support product registration in the United States.

# 1.2. Rationale for Study Design, Dose, and Control Groups

This study is a 12 week double-blind, vehicle-controlled treatment study in which subjects will be randomized to receive tapinarof cream, 1% or vehicle cream once daily for 12 weeks. The study will be conducted at multiple study centers in more than 1 country to enhance the possibility of inclusion of a wider range of population groups and to increase generalizability of the results.

The randomized, double-blind, vehicle-controlled study design will minimize the potential for subjective bias related to possible identification of which subjects are receiving active treatment and will minimize selection and allocation bias by balancing potential prognostic factors. The 12-week treatment endpoint is expected to be an adequate duration to measure full response to treatment. Clinical studies in skin conditions have historically shown a notable vehicle (as well as placebo) response rate, which could be attributable to the effects of skin moisturization or to the increased emphasis on proper skin care while participating in a clinical study. A vehicle control group is included to provide a control for comparison and to ensure study sensitivity for characterization of the safety and efficacy profile of tapinarof cream, 1%.

Subjects who complete this Phase 3 study will have the option to enroll in a separate open-label long-term safety and efficacy study for an additional 40 weeks of treatment. Subjects who do not enroll in the open-label long-term study will complete a follow-up visit approximately 4 weeks after end of treatment in this study (at Week 16).

Tapinarof cream has been investigated in prior studies at concentrations from 0.5% to 8.0% and at once daily and twice daily dosing frequencies. The 1% concentration applied once daily was chosen as the dose and dosing frequency to take forward in the clinical development program based on the data from GSK Phase 2b clinical Study 203120. In that study, applications of tapinarof at concentrations of 0.5% and 1% applied once or twice daily were evaluated. Overall, both concentrations demonstrated an acceptable safety profile when applied once or twice daily. A faster onset of action was observed with 1% dosing groups compared with the 0.5% dosing groups in both studies; fast onset of action is an important consideration for topical medications. A once daily application regimen may reduce systemic exposure as the skin heals, thereby providing a better safety profile for a drug intended for long-term use to treat a chronic condition. In addition, once daily application may improve treatment adherence compared with more frequent dosing administrations. Based on the efficacy and safety data from Study 203120, 1% once daily was chosen as the tapinarof concentration and dosing frequency to be investigated in this study and intended for registration.

### 1.3. Potential Risks and Benefits

To assess any potential impact on subject eligibility with regard to safety, the Investigator must refer to the current version of the tapinarof Investigator's Brochure for detailed information regarding warnings, precautions, contraindications, AEs, and other significant data pertaining to the study drug being used in this study.

#### 1.3.1. Risk Assessment

### 1.3.1.1. Dermatological Adverse Events, Including Skin Irritation or Allergic Reaction

Tapinarof or its excipients may induce skin irritation. Allergic or irritant reactions in the exposed areas may present as erythema, edema, papules, or vesicles. In the event of pronounced

skin reaction, spreading of the eczematous reaction beyond the original application site(s) and/or more generalized (remote) skin reactions may be observed.

In the dose-ranging Study 203120 in psoriasis, the most frequently reported dermatologic AEs were folliculitis and contact dermatitis. In the dose-ranging study 203121 in AD, the most frequently reported dermatologic AEs were folliculitis and AD. Nonclinical dermal toxicity studies of up to 8% tapinarof for up to 13 weeks indicated local effects are primarily mild-to-moderate skin irritation that is reversible; tapinarof did not show evidence of sensitization. In initial clinical studies using a different formulation of tapinarof (Formulation C), AEs of skin hyperpigmentation, application site dermatitis, papular rash, pruritus, contact dermatitis, folliculitis, erythema, and skin burning sensation were reported.

To mitigate these potential risks, subjects with a known or suspected intolerance to tapinar of or its excipients will be excluded from enrollment. Subjects' skin will be evaluated routinely for signs of irritation or allergic reaction, and if needed, study treatment may be interrupted and an appropriate treatment provided.

### 1.3.1.2. Systemic Adverse Events

Nasopharyngitis and headache were the most frequently-reported nondermatological AEs in dose-ranging Study 203120 in psoriasis. In dose-ranging Study 203121 in AD, the most frequently reported nondermatological AEs were nasopharyngitis, upper respiratory tract infection, and headache. In the initial clinical studies (in AD and psoriasis) using a different tapinarof formulation (Formulation C), nasopharyngitis, and headache were the most frequently reported nondermatological AEs. In the open-label PK Study 201851 with BID dosing of Formulation F of tapinarof cream (n=11), 1% and 2%, headache was the most frequently reported during the study (reported for 100% and 60% of subjects at the 1% and 2% doses, respectively).

In a nonclinical study in minipigs using intravenous (IV) administration, reversible decreases in arterial blood pressure and PR interval were observed; however, in this study and repeat dermal toxicity studies, there were no effects on QT interval or heart rate. Repeat-dose dermal toxicity studies also showed findings related to the liver (increased weights and hepatocellular hypertrophy/regeneration) and thymus (thymic cortex depletion in adult rabbits and rats; changes in thymus weight, microscopic decreased cellularity, and changes in thymic T cell maturation in juvenile rats) with associated secondary hematological findings. Thymic findings were also noted in repeat adult and juvenile rat studies; however, there were no clinically relevant AEs/serious adverse events (SAEs) reported.

To mitigate potential systemic risks, subjects will be monitored for AEs and any abnormal vital signs, physical examination, and laboratory test results.

## 1.3.1.3. Reproductive and Developmental Toxicity

Results of embryo-fetal development studies in rats and rabbits indicated an increased risk for embryo-fetal developmental effects, as evidenced by an increase in post-implantation loss and incidence of fetal skeletal variations. Results of a juvenile rat study indicated adverse microscopic changes in the form of renal pelvic dilatation in both sexes, along with reversible increases in total urinary glucose and protein excretion in males at  $\geq 10/15$  mg/kg/day tapinarof (administered subcutaneously).

An investigative study in rats suggested an increased risk for hydronephrosis during a narrow window of postnatal sensitivity prior to postnatal day (PND) 32 (specifically PND 15 to 21). Rat renal tubule anatomic maturation and nephrogenesis occurs during this period (Cappon, 2010; Frazier, 2013; Zoetis, 2003), however tubule morphogenesis/nephrogenesis occurs entirely prenatally in humans (Cappon, 2010; Zoetis, 2003).

To mitigate these potential risks, women of childbearing potential must utilize abstinence or a highly effective method of contraception consistently and correctly during the study and for 4 weeks after the end of treatment (Section 4.2). Monthly pregnancy testing will be conducted. Pregnant women and subjects under 18 years of age will be excluded from the study. If a woman becomes pregnant during the study, she will immediately discontinue study treatment. Additionally, AEs will be monitored and clinical laboratory testing will be performed.

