### Diagnosis and Main Criteria for Inclusion:

#### **Inclusion Criteria**:

Each subject must meet all of the following criteria to be eligible to participate in the study:

- 1. Male and female subjects ages 18 to 75 years with clinical diagnosis of chronic plaque psoriasis and stable disease for at least 6 months prior to the study.
- 2. Body surface area (BSA) involvement  $\geq 3\%$  and  $\leq 20\%$  (the subject's scalp, palms, fingernails, toenails, and soles should be excluded from the percent of total BSA (%BSA) calculations).
- 3. A Physician's Global Assessment (PGA) score of 2 (mild), 3 (moderate) or 4 (severe) at screening and baseline (pre-randomization). Subjects with mild and severe psoriasis will be limited to approximately 10% each of the total randomized population; the majority of the enrolled subjects (approximately 80%) will have a PGA of 3, signifying moderate disease.
- 4. Females of child-bearing potential and male subjects who are engaging in sexual activity that could lead to pregnancy must use at least 1 of the following adequate birth control methods while on study and for 4 weeks after the last exposure to study drug. Acceptable contraception methods are:
  - Male partner with vasectomy, OR
  - Male condom AND partner use of 1 of the contraceptive options below:
    - Spermicide
    - Contraceptive subdermal implant that meets effectiveness criteria including a < 1% rate of failure per year, as stated in the product label
    - Intrauterine device or intrauterine system that meets effectiveness criteria including a < 1% rate
      of failure per year, as stated in the product label

    - Oral contraceptive, either combined or progestogen alone
    - Injectable progestogen
    - Contraceptive vaginal ring
    - Percutaneous contraceptive patches

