### 4.2. Inclusion Criteria

Each subject must meet all of the following criteria to be eligible to participate in the study:

- 1. Male and female subjects ages 18 to 75 years with clinical diagnosis of chronic plaque psoriasis and stable disease for at least 6 months prior to the study
- 2. Body surface area involvement  $\geq 3\%$  and  $\leq 20\%$  (the subject's scalp, palms, fingernails, toenails, and soles should be excluded from the %BSA calculations).
- 3. A PGA score of 2 (mild), 3 (moderate) or 4 (severe) at screening and baseline (pre-randomization). Subjects with mild and severe psoriasis will be limited to approximately 10% each of the total randomized population; the majority of the enrolled subjects (approximately 80%) will have a PGA of 3, signifying moderate disease.
- 4. Females of child-bearing potential and male subjects who are engaging in sexual activity that could lead to pregnancy must use at least 1 of the following adequate birth control methods while on study and for 4 weeks after the last exposure to study drug. Acceptable contraception methods are:
  - Male partner with vasectomy, OR
  - Male condom AND partner use of one of the contraceptive options below:
    - Spermicide
    - Contraceptive subdermal implant that meets effectiveness criteria including a < 1% rate of failure per year, as stated in the product label
    - Intrauterine device or intrauterine system that meets effectiveness criteria including a < 1% rate of failure per year, as stated in the product label

    - Oral contraceptive, either combined or progestogen alone
    - Injectable progestogen
    - Contraceptive vaginal ring
    - Percutaneous contraceptive patches

NOTE: Subjects using hormonal contraceptives must have been on a stable dose for at least 4 weeks before baseline.

These allowed methods of contraception are only effective when used consistently, correctly and in accordance with the product label. The Investigator is responsible for ensuring that subjects understand how to properly use these methods of contraception.

Non-child-bearing potential is defined as premenarchal or pre-menopausal females with a documented bilateral tubal ligation, bilateral oophorectomy (removal of the ovaries) or

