**Tapinarof** 

hysterectomy, or hysteroscopic sterilization; or postmenopausal females defined as a cessation of menses for at least 12 months without an alternative medical cause. In questionable cases a blood sample with simultaneous follicle stimulating hormone (FSH) > 40 IU/mL is confirmatory. Documented verbal history from the subject is acceptable.

Subjects who are abstinent are eligible, but they must agree to use one of the birth control methods listed above if they start engaging in sexual activity that could lead to pregnancy during the study.

Female subjects of childbearing potential must have a negative serum pregnancy test at Screening and negative urine pregnancy test at Baseline (Day 1).

5. Capable of giving written informed consent, as applicable, which includes compliance with the requirements and restrictions listed in the informed consent form (ICF); written informed consent must be obtained prior to any study related procedures.

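### Protocol 1.3.1.3 relies on highly effective contraception for the embryo-fetal risk, but the criterion it cites (4.2, criterion 4) asks only for an adequate method and sets no effectiveness condition for most options

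*Protocol*

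**What the plan says.** Protocol Section 1.3.1.3 (Reproductive and Developmental Toxicity) reports that embryo-fetal studies in rats and rabbits "indicated an increased risk for embryo-fetal developmental effects, as evidenced by an increase in post-implantation loss". To mitigate this, it says that "women of childbearing potential must utilize abstinence or a highly effective method of contraception consistently and correctly during the study". The same sentence extends the requirement to 4 weeks beyond the last treatment and refers the reader to Section 4.2.

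Section 4.2, criterion 4, covers females of child-bearing potential and male subjects whose sexual activity makes conception possible. It says that they "must use at least 1 of the following adequate birth control methods while on study". The obligation again runs on until 4 weeks have passed since the last exposure. There are two routes: a male partner with a vasectomy, or "Male condom AND partner use of one of the contraceptive options below". Spermicide heads the list of partner options. The first option with an effectiveness condition is "Contraceptive subdermal implant that meets effectiveness criteria including a < 1% rate of failure per year", and the intrauterine device or system carries the same condition. The remaining options carry none. The criterion adds that "Subjects who are abstinent are eligible, but they must agree to use one of the birth control methods listed above" if they become sexually active.

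The synopsis repeats the criterion, including "Male condom AND partner use of 1 of the contraceptive options below". Appendix 9 (the amendment summary) lists no change to this criterion.

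**The concern.** Both statements are mandatory and cover the same women, but they describe the required level of protection differently. A reader who follows the cross-reference from the risk section does not find the term highly effective in Section 4.2. What is there is a list described as adequate, which includes options with no effectiveness condition.

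Sites enrol against Section 4.2. An ethics committee weighing the reproductive risk reads Section 1.3.1.3, and the benefit-risk conclusion in Section 1.3.3 rests on the measures taken to minimize risk. If eligibility admits a weaker safeguard than the risk section describes, that conclusion leans on something the criterion does not secure. Pregnancy testing and stopping treatment on pregnancy do not replace contraception here, because both act only after conception.

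**Working it through.** No rate, sample size or power figure is involved, so the check is a comparison of the current texts.

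| Element | Section 1.3.1.3 | Section 4.2, criterion 4, and synopsis | Agree? |
|---|---|---|---|
| Level required | highly effective | adequate | No |
| Abstinence | accepted | accepted | Yes |
| Period after treatment | 4 weeks | 4 weeks | Yes |
| Definition of the level | none; refers to Section 4.2 | none for the list as a whole; below 1% failure per year for some options | Not resolved |

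**Step 1: count the routes in criterion 4.** The partner options paired with a condom are spermicide, implant, intrauterine device or system, oral contraceptive, injectable progestogen, vaginal ring and patch, which makes 7. Adding the vasectomy route gives 7 + 1 = 8.

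**Step 2: count those with a stated effectiveness condition.** The implant and the intrauterine option carry one, which makes 2. That leaves 8 − 2 = 6 routes without one. This counts what the text states. It does not rank the methods.

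**Step 3: ask whether criterion 4 entails the Section 1.3.1.3 standard.** It would if Section 4.2 said that every listed route counts as highly effective, or if one threshold applied to the whole list. Neither is stated. A woman whose partner uses a condom while she uses spermicide satisfies criterion 4, and nothing in the protocol shows that she satisfies Section 1.3.1.3.

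**Step 4: look for text that settles it elsewhere.** The synopsis matches Section 4.2, so this is not a slip in one copy. Section 1.3.1.3 names other measures: monthly pregnancy testing, exclusion of pregnant women, and stopping treatment on pregnancy. Table 1 schedules tests at Screening, Baseline, Weeks 4, 8, 12 and 16, and Early Termination. Exclusion criterion 11 and Sections 4.6.1 and 8.5 carry the rest. These measures are consistent across the protocol, but none defines the contraception standard.

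**The case against.** The best answer is that the cross-reference itself makes the Section 4.2 list the meaning of highly effective. There is support for this. Section 1.3.1.3 is introductory text that defers to Section 4.2, both places speak of consistent and correct use, and both give the same 4-week period. Every route other than vasectomy also pairs the condom with a second method. This reading is possible, but the protocol does not state it. The list is called adequate, and a failure-rate condition is set for only some options, so a reader cannot tell whether equivalence was intended.

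Three stronger readings are tempting and should not be drawn:

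- **That condom plus spermicide fails the standard.** The protocol does not define highly effective, and the below-1% condition is attached to particular options rather than offered as the definition. Calling the combination inadequate would need a classification of methods from outside the documents.
- **That every woman of child-bearing potential is affected, or that the described mitigation is not what is enrolled.** Abstinent women are treated alike in both places. Women using an option with the below-1% condition are not in evident conflict. Condom plus spermicide is permitted, not required.
- **That sites have no standard to apply.** They have criterion 4. Section 4.1 prohibits violations of the inclusion criteria, and Section 6 disallows waivers except for immediate safety concerns. The gap lies between that operative criterion and the risk section's description of it.

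**Conclusion.** The inconsistency is real and present in Protocol Version 2.0. Section 1.3.1.3 describes the contraceptive safeguard as highly effective. The criterion it cites asks for an adequate method and states an effectiveness condition for 2 of its 8 routes. Eligibility therefore does not guarantee the described safeguard for non-abstinent women who use an option without a stated threshold.

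The number of such women cannot be computed, because the documents give neither the expected number of women of child-bearing potential nor their methods. The conclusion rests on the protocol's wording alone and assumes no external ranking of methods.

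The point is limited in scope: no endpoint, sample size, power figure or analysis depends on it. It is still more than clerical, because it concerns a mandatory safeguard for a named embryo-fetal risk that the benefit-risk statement relies on. It should be corrected.

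**What to change.** Reconcile Protocol Section 1.3.1.3, Section 4.2 criterion 4 and the synopsis so that all three state one contraception standard in the same words, with one method list that meets it. If the sponsor means the Section 4.2 list to be what Section 1.3.1.3 calls highly effective, the text should say so. Otherwise the passages should be brought into line with each other. Which standard applies is for the clinical and regulatory team, and this review takes no position on it.

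The cost is a wording amendment in three places, plus a check that the consent form matches. The consent pages are not in the reviewed file, so whether they need changing cannot be judged here. The SAP needs no change.
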